A home-based intervention to promote mindful breathing awareness through pursed-lip breathing training for COPD patients

NCT05349123

June 8, 2021

Site Principal Investigator: [name]
Protocol version number and date: June 8, 2021, Version 3

Hypothesis:

We hypothesize that providing COPD patients with a mindful breathing module that is easy-to-use, prompts them to complete daily mindful breathing practice, and provides feedback will improve their breathing mechanics, emotional awareness, increase the time that they spend in heart rate coherence, and improve their quality of life.

Aims, purpose, or objectives:

The primary outcomes of the study are changes in breathlessness and emotions. Changes from baseline to three months on the two primary outcomes will be compared between the study arms using two-sample, two-sided t-tests with 5% type I error rates. Means, SDs, medians, ranges, and frequency distributions will be reported and plotted over time by study arm. Linear models will be used to assess the impact of treatment arm on three-month outcomes after adjusting for the corresponding baseline measure and other variables related to the outcome (age, degree of breathlessness at baseline using the mMRC dyspnea, and FEV1).

Methods:

This project will involve two Phases: phase one in which mindful breathing by itself without any other device will be tested to make sure that it is acceptable to patients and makes a difference comparing to the usual protocol in use right now. Phase two will include a particular device that will guide the mindful breathing practice that we think will be more intuitive to practice and guide the mindful breathing and that device will be tested once we know that the acceptance to the mindful breathing practice, from phase one, is appropriate.

Phase 1: A total of 70 adults diagnosed with COPD will be enrolled in the study. Half of the participants will be randomized to receive the home-based PR with the Pursed Lipped Breathing Application (intervention) and half will receive the home-based PR (control). Randomization will take place in a REDCap database and will be in equal proportion.

Phase 2: A total of 70 adults diagnosed with COPD will be enrolled in the study. Half of the participants will be randomized to receive the home-based PR with the mindful breathing module which consists of the Pursed Lipped Breathing Application and the Spire Health Tags (intervention) and half will receive the home-based PR (control). Randomization will be take place in a REDCap database and will be in equal proportion.

Both groups entail one week of baseline where the participants wear an ActiGraph activity tracker and answer questionnaires. Baseline is followed by 12 weeks of home-based PR plus health coaching. The Intervention group also has the mindful breathing module loaded on the Android tablet. Both groups will also complete questionnaires and wear an ActiGraph activity monitor at 3 and 6 months.

Questionnaires:

Quality of Life will be assessed three times (baseline, 3 and 6 months) by the Medical Research Council (mMRC) questionnaire, the Chronic Respiratory Disease Questionnaire (CRQ), the Self-Management Ability Scale (SMAS30) and the Mindful Attention and Awareness Scale (MAAS). The questionnaires take about 20 minutes to complete.

At baseline additional health data will be collected from the medical record (chart review) to complete the Charlson comorbidity index, including lung function, demographics, living condition (living alone or not), GOLD stage, and comorbidities.

ActiGraph:

Physical activity will be measured three times (baseline, 3 and 6 months) by the ActiGraph activity monitor. The ActiGraph activity monitor has tri-axial accelerometers and will be wrist worn for seven days. Important measures to be analyzed are daily number of steps, activity counts, minutes per day spent in daily physical activities of at least moderate intensity, and sedentary time (<2 metabolic equivalents).

The questionnaires and Acti Graphs will be mailed to the participant with pre-paid shipping materials to send back.

Health Coaching:

All participants will receive a weekly coaching call to discuss their rehabilitation and health process. The calls are structured using motivational interviewing. The coach will review with the patient the data from the health coach system. Collaboratively, goals for rehabilitation for the following week will be set, based on information gathered and the patients' personal preferences. Each call lasts about 20 minutes. All calls will be taped to ensure compliance with the protocol.

Target accrual: 140

Subject population (children, adults, groups): Adults 40 years of age or older

Inclusion Criteria:

- Clinical diagnosis of COPD
- At least 10 pack years of smoking

Exclusion Criteria:

- Unable to do mild exercise (orthopedic-neurologic problems or confined to a bed)
- Unable to follow commands (cognitive impairment)
- Have a high likelihood of being lost to follow-up (active alcohol or drug abuse)
- Live in an area that does not have cellular service (Verizon)

Potential participants will have the option of meeting a study coordinator in person (if they are on campus for a clinical appointment), meeting via Video Anywhere through Epic, or meeting over the phone. If the patient desires, their consent can be digitally obtained and documented through PTRAX. The patient also has the option of receiving the consent via mail and mailing back the consent in a provided postage paid envelope. Documentation of informed consent/HIPAA authorization will involve the use of the Research Participant Tracking (PTrax) Digital Signature Capture technology for research informed consent/HIPAA authorization forms. This is an institutionally approved process for documenting consent/HIPAA authorization only while the subject, and/or the subject's representative, is in the physical presence of the person authorized to obtain consent/HIPAA authorization. The study team may print a copy of the signed consent form/HIPAA authorization form for the subject or their representative. The consent form/HIPAA authorization form will also be available to the subject via the patient portal.

Note: If the subject or their representative prefers not to use the Digital Signature Capture technology, the study team will provide a paper consent form/HIPAA authorization form for signature.

Statistica Analysis Plan

Sample Size

We calculated that sixty two participants will provide 80% power to detect 1 point of change in the two co primary outcomes (breathlessness and emotion as measured by the CRQ) with an alpha of 0.025. A 1 point change represents a clinically meaningful change.⁹⁵ We expect about a 20 percent attrition rate (withdraw, not able to complete the 12 weeks of home-based rehab) and will therefore enroll 70 participants in each phase.

Analysis Plan

The primary outcomes of the study are changes in breathlessness and emotions. Changes from baseline to three months on the two primary outcomes will be compared between the study arms using two-sample, two-sided t-tests with 5% type I error rates. Means, SDs, medians, ranges, and frequency distributions will be reported and plotted over time by study arm. Linear models will be used to assess the impact of treatment arm on three-month outcomes after adjusting for the corresponding baseline measure and other variables related to the outcome (age, degree of breathlessness at baseline using the mMRC dyspnea, and FEV1).

The Chronic Respiratory Disease Questionnaire (CRQ) is a 20-question inventory assessing the areas of dyspnea, fatigue, emotion, and feelings of mastery. The fatigue, emotion, and mastery subscales ask patients to rate how often in the last two weeks they have been afflicted with a particular feeling or experience on a scale of 1 to 7, with higher ratings indicating less symptom impairment. The CRQ has shown to be valid and has high internal consistency reliability. Test-retest reliability is adequate in all subscales, but is particularly high in the subscales of fatigue ($r=0.90$), emotion ($r=0.93$), and mastery ($r=0.91$). The minimal clinically important difference for this instrument of 0.5 points is universally recognized. The Domains Dyspnea (breathlessness) and Emotions are the two co primary outcomes.

Physical activity will be measured at baseline, 3, and 6 months by the ActiGraph GX6 activity monitor, which has been used to assess physical activity in COPD populations. (92) The number of daily steps at baseline, 3, and 6 months and across the two groups will be compared. Emotional Intelligence will be measured by the Trait Emotional Intelligence questionnaire at baseline, 3, and 6 months .(84) Mindfulness will be measured by the Mindful Attention and Awareness Scale at baseline, 3, and 6 months.(93) The participants HRC and respiratory rate will be tracked for the entire intervention period using the Spire Health Tags. At baseline additional health data will be collected from each participant's medical record to complete the Charlson comorbidity index, including lung function, demographics, living condition (living alone or not), GOLD stage, and comorbidities.

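### Is each phase too small because it is sized for 1 CRQ point while the SAP cites a minimal important difference of 0.5?

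*Combined protocol and SAP*

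**What the plan says.** Sample Size states that 62 participants give "80% power to detect 1 point of change in the two co primary outcomes", namely breathlessness and emotion on the CRQ, at an alpha of 0.025. It adds, with a citation: "A 1 point change represents a clinically meaningful change". Enrolment is 70 in each phase.

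The Analysis Plan, describing the same instrument, says: "The minimal clinically important difference for this instrument of 0.5 points is universally recognized". On testing it says: "Changes from baseline to three months on the two primary outcomes will be compared between the study arms using two-sample, two-sided t-tests", at a 5% type I error rate. It also plans linear models for the three-month outcomes, adjusted for baseline and other covariates.

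Under Methods, phase 1 is to "make sure that it is acceptable to patients and makes a difference comparing to the usual protocol in use right now". Phase 2 follows once acceptance of the practice in phase 1 is known to be appropriate. Of both groups, Methods says: "Baseline is followed by 12 weeks of home-based PR plus health coaching". The arms differ in one respect: "The Intervention group also has the mindful breathing module loaded on the Android tablet".

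**The concern.** The SAP names two benchmarks of clinical importance, 0.5 and 1 point, and sizes the trial on the larger without linking them. Both arms receive rehabilitation and coaching, so the full point would have to come from the added breathing component alone. If that component adds 0.5, the primary test of each outcome would more often than not be non-significant. A reader who saw only the 1-point statement might then take a null phase 1 as ruling out any worthwhile benefit, although the confidence interval would often still include 0.5. The question of whether the practice makes a difference would look answered when it was not.

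**Working it through.** **Inputs.** From Sample Size: 62 participants (31 per arm under equal allocation), 80% power, a difference of 1 point, and alpha 0.025 with sidedness not stated. From the Analysis Plan: two-sided t-tests at 5%, and a minimal important difference of 0.5. No SD is given.

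**The plan's own figure.** Without an SD, 62 cannot be rebuilt from its inputs. One can only solve for the SD that makes it true:

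SD = 1 / [(z_alpha + 0.842) × √(2/31)], with √(2/31) = 0.2540.

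- Alpha 0.025 two-sided: 1 / (3.083 × 0.2540) = 1.277 (noncentral t: 1.250).
- Alpha 0.025 one-sided, equivalent to 0.05 two-sided: 1 / (2.802 × 0.2540) = 1.405 (noncentral t: 1.383).

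These SDs are implied, not stated, so the 80% is neither confirmed nor contradicted.

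**Power at 0.5.** Halving the difference halves the standardised effect:

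Power = Φ[(z_sizing + 0.842)/2 − z_test].

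| Sizing alpha | Test alpha | Calculation | Power at 0.5 |
|---|---|---|---|
| 0.025 two-sided | 0.025 two-sided | Φ(1.541 − 2.241) | 24.2% |
| 0.025 one-sided | 0.05 two-sided | Φ(1.401 − 1.960) | 28.8% |
| 0.025 two-sided | 0.05 two-sided | Φ(1.541 − 1.960) | 33.8% |

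The third row pairs the sizing alpha, read as two-sided, with the test the Analysis Plan states. The noncentral t gives 24.2%, 28.8% and 34.1%.

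**What drives the result.** The formula contains only the alphas and the 80%. N, the SD and the scale all cancel; with 62 per arm the first two rows are again 24.2% and 28.8%. Every trial with 80% power at its target has this power at half its target, so the figure reveals no fault particular to this plan.

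**Precision.** With 31 per arm the half-width of the interval for the difference is 0.635 (95%, SD 1.250), 0.702 (95%, SD 1.383) or 0.730 (97.5%, SD 1.250). An observed difference of zero would not exclude 0.5.

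**The statements side by side.** A difference can be minimal at 0.5 and clearly meaningful at 1 point, so the two sentences are compatible. The plan claims no power at 0.5, so no such claim fails. It has no rule that turns a non-significant result into a finding of no difference. Its stated condition for phase 2 is acceptance.

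**The case for a change.** The strongest case for the concern is that the SAP itself calls 0.5 the minimal important difference, gives no reason to expect twice that on top of an active programme, and does not report power at 0.5. Other readings raise that power only modestly. With 56 completers (70 × 0.8) it is 22% at two-sided 0.025. If the 80% is joint power for both outcomes, assumed independent, it is 31% per outcome at 0.025, or 42% tested at 5%.

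The arithmetic stands, and so does the caution: a non-significant phase 1 would not rule out 0.5. The step from there to a defect does not stand.

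- Powering above the minimal difference is legitimate. The source cited for 1 point cannot be judged from the documents.
- The Analysis Plan does not say whether 0.5 is a within-patient or a between-arm figure, so using it as a between-arm target is an assumption.
- The misreading needs a reader who overlooks the 0.5 in the very next section. Failure to reject in a superiority test does not show absence of effect at any sample size.
- Per-outcome power understates the chance of some positive finding if either outcome suffices. With both effects at 0.5 and independent, that chance is 1 − (1 − 0.242)² = 43% at 0.025, or 1 − (1 − 0.341)² = 57% at 5%. Correlation between the outcomes lowers both.

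The differing alphas (0.025 and 5%) and the attrition allowance (56 completers against 62) are separate matters, not settled here.

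**Conclusion.** The concern does not hold. Power at a between-arm difference of 0.5 is about 24% to 34%, taking the plan's 80% as correct, per outcome, with 31 analysed per arm in an unadjusted test. That follows from choosing 1 point as the target, a choice the plan makes openly and supports with a citation. No stated figure or rule is shown to be wrong, and no planned analysis or decision would change.

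Writing the power at 0.5 into Sample Size would be optional detail. It would also require a back-solved SD and a choice between alphas that the documents do not reconcile. Resizing for 0.5 would need about (1/0.5)² × 62 = 248 evaluable participants per phase, and no stated aim specifies detection of 0.5. When results are reported, the estimated difference and its interval should be read in the ordinary way. The planned tests and models already provide both.

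### 62 needed, about 20% attrition and 70 enrolled per phase do not agree: 70 leaves 56 evaluable, which gives about 75% power, not 80%, at the sizing alpha of 0.025 if the 62 and the 20% are right.

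*Combined protocol and SAP*

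**What the plan says.** All three figures stand in the Sample Size section of the SAP.

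- Requirement: "We calculated that sixty two participants will provide 80% power to detect 1 point of change in the two co primary outcomes". The alpha is 0.025, with no statement of whether it is one- or two-sided. No SD is given.
- Attrition: "We expect about a 20 percent attrition rate (withdraw, not able to complete the 12 weeks of home-based rehab"). The definition counts people who do not complete the 12-week programme as well as those who withdraw.
- Enrolment: the investigators "will therefore enroll 70 participants in each phase". The wording presents 70 as derived from the first two figures.

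The Methods section repeats 70 for each phase, with equal allocation (35 per arm), and the target accrual is 140. The Analysis Plan, and the same text under the aims, compares change from baseline to three months by "two-sample, two-sided t-tests with 5% type I error rates" for each of the two co-primary CRQ domains.

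**The concern.** An enrolment target that allows for attrition should return the required number once the expected losses are taken off. Here it does not: a fifth of 70 is 14, and 70 − 14 = 56, which is 6 short of 62. The gap is too large for rounding or for the word 'about' to cover.

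What is at stake is the power claim for both phases. If 62 is the true requirement and a fifth are lost, the design falls short of its stated power. If 56 was the true requirement, the design is sound and the 62 is an error. With no SD stated, nobody can settle this from the document, and a reader of a null result would not know what size of effect the trial was built to detect.

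**Working it through.** **Inputs.** From the Sample Size section: 62 evaluable per phase (read as a total, 31 per arm), 80% power, a 1-point difference, alpha 0.025, about 20% attrition, 70 enrolled. From Methods: equal allocation. From the Analysis Plan: two-sample t-test on change.

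**1. Can 70 be reproduced?**

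- Standard inflation, N/(1 − d): 62/(1 − 0.20) = 77.5, so 78.
- Cruder inflation, N × (1 + d): 62 × 1.20 = 74.4, so 75.
- Backwards from 70: 70 × (1 − 0.20) = 56.
- Attrition that 70 can absorb while keeping 62: 1 − 62/70 = 11.4%.

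Neither formula gives 70. However, 56/0.80 = 70 exactly, so 70 would be correct had the requirement been 56.

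**2. The SD implied by the 62.** The 62 cannot be checked directly because no SD is given. It can be used to calibrate. For a two-sample t-test with n per arm, the noncentrality is (δ/SD) × √(n/2) on 2n − 2 degrees of freedom. Setting n = 31, δ = 1 and power 80%, and solving for SD:

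- Two-sided 0.025: standardised difference 0.800, SD 1.25.
- One-sided 0.025: standardised difference 0.723, SD 1.38.

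By construction, each reproduces 80.0% power at 62.

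**3. Power with 56 evaluable (28 per arm), holding that SD.**

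| Reading of alpha 0.025 | Implied SD | Power at 62 | Power at 56 | Difference detectable with 80% power at 56 |
|---|---|---|---|---|
| Two-sided | 1.25 | 80.0% | 75.2% | 1.05 points |
| One-sided | 1.38 | 80.0% | 75.7% | 1.05 points |

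The normal approximation gives 75.4% and 75.9%. The result hardly depends on the missing SD, because the SD is fixed by the plan's own 62 and 80%.

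**4. Sensitivity to attrition** (70 enrolled, two-sided 0.025, SD 1.25, whole participants, rounded down).

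| Attrition | Evaluable | Power |
|---|---|---|
| 10% | 63 | 80.7% |
| 15% | 59 | 77.7% |
| 20% | 56 | 75.2% |
| 25% | 52 | 71.6% |

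**5. The test in the Analysis Plan.** At two-sided 5% with SD 1.25, 56 evaluable gives 83.6%. If the sizing alpha was one-sided 0.025, it has the same upper critical value as a two-sided 5% test, the implied SD is 1.38, and power is 75.7%.

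**6. If 56 was the requirement.** The SD that gives 80% power at 28 per arm is 1.19 (two-sided 0.025) or 1.31 (one-sided).

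**The case against.** Five points can be made for the plan.

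*The shortfall is conditional.* If 56 was the real requirement, or if true attrition is about 11%, 80% power stands. This is correct. What is established without condition is that the three figures disagree; the 75% holds only if the 62 and the 20% are both right.

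*The planned test may be adequately powered anyway.* If the sizing used two-sided 0.025 and each outcome is tested at two-sided 5%, power at 56 is 83.6%. That depends on a sidedness the plan does not state, and the gain comes from giving up the stricter alpha used for sizing. Under the one-sided reading the gain disappears and power is 75.7%. Under neither reading do 62, 20% and 70 agree.

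*More than 56 may be evaluable.* Questionnaires are mailed with prepaid return, and the Methods say "Both groups will also complete questionnaires and wear an ActiGraph activity monitor at 3 and 6 months", so some people who stop rehabilitation may still supply a three-month CRQ. This is a fair mitigation. But the plan's own attrition definition counts non-completers as lost and enlarges enrolment on that account.

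*Covariate adjustment may recover the loss.* The linear models adjust for baseline and other variables, and a reduction of about 10% in residual variance would restore 80% power at 56: 1 − (0.800/0.844)² ≈ 0.10, where 0.844 is the standardised difference needed with 28 per arm. The plan gives no correlation to support a figure and powers the trial on the two-sample comparison, so this cannot be credited as it stands.

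*The loss is small.* It is under 5 percentage points. That limits the severity, but it does not make the statement correct.

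**Conclusion.** The concern holds. The 70 per phase does not follow from 62 needed and about 20% attrition under either usual inflation formula, and nothing elsewhere in the document reconciles them. If the 62 and the 20% are right, each phase has about 75% power at the sizing alpha (75.2% two-sided, 75.7% one-sided), equivalent to 80% power for about 1.05 points instead of 1. This assumes equal arms, 62 read as a total per phase, and 56 evaluable under the plan's attrition definition. Reading 62 as per arm would mean 124 per phase and a larger mismatch.

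Which of the three figures is wrong cannot be decided from the document. The error affects the justification of the sample size and how a null result would be read. It does not invalidate the design or the analysis. It should be fixed.

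**What to change.** In the Sample Size section:

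1. State the assumed SD of the change score, and whether alpha 0.025 is one- or two-sided. Explain how it relates to the 5% tests in the Analysis Plan.
2. Say which of 62, 20% and 70 is wrong, and restate the paragraph accordingly:
   - *62 and 20% stand, enrolment stays at 70:* say that 70 enrolled with about 20% attrition leaves 56 evaluable, giving about 75% power for a 1-point difference at alpha 0.025, or 80% power for about 1.05 points. Replace these figures with ones from the sponsor's own SD once it is stated.
   - *The requirement was 56:* replace sixty-two with 56 and give the SD that supports it (about 1.19 if two-sided 0.025, about 1.31 if one-sided).
   - *The 20% is wrong:* give the attrition figure that fits, about 11%, with its basis.
   - *The 70 is wrong:* 62 and 20% imply 78 per phase, or 2 × 78 = 156 against the target accrual of 140.
3. As a clarification, state that the mailed three-month CRQ is sought from all randomised participants, including those who stop rehabilitation.

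If 70 per phase is kept, the cost is SAP wording only, with no added enrolment. The one downside is a slightly less favourable stated power if the 62 and the 20% both stand. Only the last option under item 2 would add participants, and the correction does not require it.

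### The primary test is an unadjusted t-test on change scores; the baseline-adjusted model, which should be more precise, is left unranked and without an alpha

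*Combined protocol and SAP*

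**What the plan says.** The Analysis Plan, and the same text under Aims, purpose, or objectives, sets the primary comparison: "Changes from baseline to three months on the two primary outcomes will be compared between the study arms using two-sample, two-sided t-tests". A 5% type I error rate is attached to this test. The outcomes are identified later in the Analysis Plan: "The Domains Dyspnea (breathlessness) and Emotions are the two co primary outcomes".

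The same paragraph adds a second analysis: "Linear models will be used to assess the impact of treatment arm on three-month outcomes after adjusting for the corresponding baseline measure". Its other covariates are "age, degree of breathlessness at baseline using the mMRC dyspnea, and FEV1", which makes four with the baseline domain score. The plan does not call this model primary, secondary or sensitivity, and gives it no error rate.

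On where FEV1 comes from, the Questionnaires section says: "At baseline additional health data will be collected from the medical record (chart review) to complete the Charlson comorbidity index, including lung function". The disease criterion for entry is "Clinical diagnosis of COPD", with no spirometry requirement. The plan has no rule for a participant whose record holds no FEV1.

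The Sample Size section states that "sixty two participants will provide 80% power to detect 1 point of change in the two co primary outcomes" "with an alpha of 0.025". It expects about 20 percent attrition and enrolls 70 per phase. It gives no SD and no correlation between baseline and three months.

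**The concern.** A t-test on change is the same as adjusting for baseline with the slope forced to 1. When the correlation between visits is below 1 and the variances are similar, the best slope is below 1, and the change score carries extra baseline noise. Estimating the slope removes that noise and needs no extra data, because a change score already requires the baseline value.

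As written, the error rate belongs to the analysis expected to give the wider confidence interval, in a phase of 70 randomised participants. The plan also produces two results for each co-primary outcome without saying which one decides if they disagree.

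Promoting the planned model unchanged is not a clean solution. A complete-case fit would drop anyone without a recorded FEV1, including participants the t-test would keep.

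**Working it through.** **Inputs from the documents.** 62 evaluable participants, 80% power, a 1-point difference and alpha 0.025 (Sample Size); two-sided tests at 5% (Analysis Plan); equal allocation (Methods). 70 enrolled with 20% attrition gives 70 × 0.80 = 56 completers.

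**Assumptions.** The SD of change and r are not given. Equal variances at the two visits are assumed unless stated otherwise.

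**The plan's own figure.** With no SD stated, 62 cannot be reproduced independently, but it can be inverted. For 31 per arm, 80% power and a 1-point difference, the implied SD of change is:
- two-sided alpha 0.025: 1.25 (noncentral t) or 1.28 (normal approximation);
- two-sided alpha 0.05: 1.38 or 1.41.

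**Variance comparison.** Let s be the SD at each visit.
- Change score: 2s²(1 − r).
- Adjusted for baseline: s²(1 − r²).
- Ratio, adjusted to change: (1 + r)/2, which is below 1 for any r below 1.

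Estimating p covariate slopes multiplies the adjusted variance by 1 + p/(N − p − 3). At N = 56 this is 1 + 1/52 = 1.019 for the baseline score alone and 1 + 4/49 = 1.082 for four covariates. Power is noncentral t with N − 2 − p degrees of freedom.

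**Power for 1 point at N = 56.** The four-covariate row assumes that age, mMRC and FEV1 explain nothing beyond the baseline score, which is its worst case.

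| Setting | Analysis | r = 0.3 | r = 0.5 | r = 0.7 | r = 0.93 |
|---|---|---|---|---|---|
| SD 1.25, alpha 0.025 | t-test on change | 75.2% | 75.2% | 75.2% | 75.2% |
| | baseline only | 91.1% | 86.4% | 81.5% | 76.0% |
| | four covariates | 89.2% | 84.1% | 78.9% | 73.1% |
| SD 1.25, alpha 0.05 | t-test on change | 83.6% | 83.6% | 83.6% | 83.6% |
| | baseline only | 95.1% | 91.9% | 88.4% | 84.2% |
| SD 1.41, alpha 0.05 | t-test on change | 74.1% | 74.1% | 74.1% | 74.1% |
| | baseline only | 89.3% | 84.6% | 79.9% | 74.8% |

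A simulation of 20,000 trials per cell in the first setting agrees: 0.909, 0.861, 0.820 and 0.762 for baseline only; 0.892, 0.846, 0.785 and 0.732 for four covariates; 0.748 to 0.760 for the t-test.

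**Break-even and equivalent size (SD 1.25, alpha 0.025).** Baseline-only adjustment stops helping at r of about 0.96, and the four-covariate model, in its worst case, at about 0.84. To match the adjusted power at r = 0.5, the t-test would need 72.4 analysed participants instead of 56 for baseline only (72.4/56 = 1.29, so 29% more), or 68.2 for four covariates (22% more).

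**Unequal variances.** If the follow-up SD is k times the baseline SD, the ratio is k²(1 − r²)/(1 + k² − 2rk). Over the same r values, k = 0.8 gives 0.50 to 0.63 and k = 1.25 gives 0.78 to 0.98. The ratio reaches 1 only where r = 1/k (r = 0.8 for k = 1.25). There, baseline-only adjustment loses just the 2% slope cost.

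**Missing FEV1 (illustrative).** If 4 of 56 lacked FEV1 and were dropped, four-covariate power at r = 0.7 would be 75.0%, level with the t-test. With 6 dropped it would be 72.9%.

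**The case against.** The strongest reply is that nothing is in error. The t-test is valid, the outcomes are defined as changes, and a baseline-adjusted estimate will be reported anyway. That is right, and it limits the point to efficiency and to which result decides. It does not explain why the less precise analysis should be the one that carries the alpha.

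Second, the planned model has four covariates, whereas the larger gains belong to a baseline-only model that the plan does not contain. This stands. In its worst case the four-covariate model falls behind the t-test above r of about 0.84, which is why the baseline score is the covariate to require.

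Third, the size of the gain rests on unstated inputs. Holding the change SD at 1.25 implies a single-visit SD of 1.25/√(2(1 − r)): 1.61 at r = 0.7 and 3.34 at r = 0.93. The latter is not credible for emotion if the domain score is a mean of items rated 1 to 7. The 0.93 column therefore only marks where the gain fades. The 0.93 that the plan reports for emotion is test-retest reliability, not a correlation across 12 weeks of rehabilitation. If the single-visit SD is instead held at an assumed 1.2 (N = 56, alpha 0.025), the t-test has 78.9% against 89.2% for baseline only at r = 0.5, and 95.4% against 97.6% at r = 0.7. The gain may be material or small, and the documents cannot settle which.

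Fourth, the 75% t-test figure reflects alpha 0.025 and 56 completers, which are separate matters. At 5% it is 83.6%. The advantage of adjustment appears at either alpha.

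Finally, no document says that FEV1 will be missing, and the Analysis Plan intends lung function to come from each participant's record. The count of 4 is hypothetical, but the absence of a rule is real.

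**Conclusion.** The concern holds as a recommended improvement in precision; it is not a validity error. For the same participants, adjusting for the baseline domain score should give a narrower interval than the change-score t-test. On the assumptions shown (change SD 1.25, equal variances, 56 completers, alpha 0.025), the gain is about 16 power points at r = 0.3, 11 at r = 0.5, 6 at r = 0.7 and under 1 at r = 0.93. The direction does not depend on which alpha the sponsor adopts. The size depends on r and the SD, neither of which is stated, so confidence in the magnitude is only medium. The gain can vanish if r is very high, or if follow-up scores are more variable than baseline and r is near 0.8, but the loss from adjusting for one covariate is then about 2% in variance.

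**What to change.** In both Aims, purpose, or objectives and the Analysis Plan, name one primary analysis for each co-primary outcome: the linear model of the three-month CRQ domain score on arm and that domain's baseline score. Report the adjusted mean difference, its confidence interval and p-value at the alpha the sponsor settles on for the two co-primaries. Label the change-score t-test as supportive.

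Keep age, mMRC and FEV1 in the primary model only with a stated rule for missing chart-review FEV1, for example imputation of the baseline covariate, so that nobody is dropped. Otherwise place them in a supportive model.

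The cost is SAP wording, with no new data, visits or participants. Baseline-only adjustment uses 1 degree of freedom and inflates the variance by about 2%. The four-covariate version uses 4 and inflates it by about 8%, which could cost about 2 power points against the t-test if r is very high and the extra covariates explain nothing.
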